# Study Application (Version 1.5)

## 1.0 General Information

### \*Enter the full title of your study:

Role of Glucagon in outpatient colonoscopy? A Prospective Double-Blind randomized controlled trial.

### \*Enter the study number or study alias

Glucagon and Colonoscopy.  
\* This field allows you to enter an abbreviated version of the Study Title to quickly identify this study.

## 5.0 Initial Screening Questions - Updated 9/13

(Note: You must answer every question on this page to proceed).

If you are converting to the new form, check questions 5.4, 5.6, 5.7, 5.8 and 5.10 before saving and continuing to the next section.

### 5.1 \* Application type:

- Full Committee
- Expedited
- Exempt

### 5.2 \* Risk level (Help Text updated 9/13):

- Minimal risk
- Greater than minimal risk

### 5.3 \* Subject contact:

- Yes (including phone, email or web contact)
- No (limited to medical records review, biological specimen analysis, and/or data analysis)

### 5.4 \* Funding (past or present):

- Funded or will be funded (external sponsor, gift, program or specific internal or departmental funds)
- Unfunded (no specific funds earmarked for this project)
- Unfunded student project

### 5.5 \* The Principal Investigator and/or one or more of the key study personnel has financial interests related to this study:

- Yes  No

If **Yes**, the Conflict of Interest Advisory Committee (COIAC) office may contact you for additional information.

### 5.6 \* This is an investigator-initiated study:

- Yes  No

### 5.7 \* This study ONLY involves retrospective records review and/or identifiable biospecimen analysis:

- Yes  No

### 5.8 \* This is a clinical trial:

- Yes  No

#### Clinical Trial Registration

"NCT" number for this trial:

NCT 02078726

**5.9 \* This is a multicenter study:**

Yes  No

**5.10 \* This application involves the study of unapproved or approved drugs, devices, biologics or in vitro diagnostics:**

Yes  No

**5.11 \* This application involves a Humanitarian Use Device:**

- No
- Yes, and it includes a research component
- Yes, and it involves clinical care ONLY

**5.12 \* This study involves human stem cells (including iPS cells and adult stem cells), gametes or embryos:**

- No
- Yes, and requires CHR and GESCR review
- Yes, and requires GESCR review, but NOT CHR review

**5.13 \* This is a CIRB study (e.g. the NCI CIRB will be the IRB of record):**

Yes  No

**5.14 \* This application includes a request to rely on another IRB (other than NCI CIRB):**

Yes  No

Note: If this request is approved, the CHR will **NOT** review and approve this study. Another institution will be the IRB of record.

**6.3 Check any research programs this study is associated with:**

- Cancer Center
- Center for AIDS Prevention Sciences (CAPS)
- Global Health Sciences
- Immune Tolerance Network (ITN)
- Neurosciences Clinical Research Unit (NCRU)
- Osher Center
- Positive Health Program

## 7.0 Study Design

**7.1 \* Study design (Help Text updated 9/13):**

Glucagon transiently decreases peristalsis of smooth muscle in the gastrointestinal tract. It is widely used by radiologists to improve diagnostic yields of upper and lower GI barium contrast examinations. Glucagon is also routinely administered intravenously for all endoscopic retrograde cholangiopancreatography (ERCP) throughout the United States to facilitate cannulation of the duodenal papilla and sphincterotomy. Glucagon has been used at the dose of 1-3 mg intravenously by [name] in over 5000 ERCP examinations. However, the role of glucagon in facilitating colonoscopy remains unanswered and is not considered "routine". Several studies have evaluated the effect of glucagon on colonoscopy with varying results. No large scale randomized controlled trial has been performed to conclusively establish the effect of routine glucagon administration prior to colonoscopy. The investigators plan to carry out a randomized, double blind, placebo controlled trial that studies key parameters of a colonoscopy such as cecal intubation time, withdrawal time, total procedure time, adenoma detection rate, endoscopist's assessment of the difficulty of the procedure, patient comfort, and patient's willingness to undergo a repeat colonoscopy.

**7.2 If this is a clinical trial, check the applicable phase(s) (Help Text updated 9/13):**

- Phase I
- Phase II
- Phase III
- Phase IV

## 8.0 Scientific Considerations

**8.1 Hypothesis (Help Text updated 9/13):**

This study has a hypothesis:

Yes  No

If yes, state the hypothesis or hypotheses:

1. Glucagon will produce a decrease in colonic spasm leading to colonoscopies with improved diagnostic yield (improved adenoma detection rate), faster procedure times, and improved patient and endoscopist experience.

## 8.2 \* List the specific aims:

Identify whether glucagon administration during colonoscopy improves the following:

1. Cecal intubation time (time from anal insertion to reaching the cecum as noted by demonstrating the appendiceal orifice).
2. Colonoscope withdrawal time (time from withdrawing colonoscope from cecum to anus).
3. Total procedure time
4. Adenoma detection rate (i.e. the total number of polyps and adenomas per patient procedure)
5. Amount of sedatives used
6. Adequacy of visualization (graded by endoscopist)
7. Difficulty in scope manipulation (graded by endoscopist)
8. Presence and severity of spasms (graded by endoscopist)
9. Pain during procedure (graded by patients on the day after procedure)
10. Abdominal fullness (graded by patients on the day after procedure)
11. Acceptance of future colonoscopy (graded by patients on the day after procedure upon discharge from unit)

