## 8.3 Statistical analysis:

Matched student t-test will be used for continuous variables and the Chi-square test will be used for categorical variables. The UCSF Department of Epidemiology and Biostatistics will be involved in the formal statistical analysis.

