Colonoscopy is commonly complicated by colonic spasms, particularly in individuals consuming a low residue diet, this leading to patient discomfort, longer procedure times, increased use of sedatives and operator fatigue. Glucagon, an antispasmodic agent, has been demonstrated to reduce intraluminal colonic pressure, colonic wave activity and colonic motility index and is routinely administered prior to colonoscopy by some gastroenterologists. As mentioned above, intravenous glucagon is routinely used during every ERCP examination throughout the United States of America. However, its effect on duration of colonoscopy, adenoma detection rate, patient comfort and operator fatigue has not been definitively answered. There are four previous studies that have evaluated the use of glucagon during colonoscopy and produced conflicting result. Three of these studies were performed prior to 1995 and cannot account for technological improvement leading to improved colonoscope performance. For instance, the first study performed in 1978 took an average of 50 minutes to perform a colonoscopy, almost twice as long as a colonoscopy performed today. Furthermore, each study was limited by small sample sizes (~30 subjects in each study group) and produced conflicting results. One of the studies demonstrated that glucagon decreases total colonoscopy time while the other two studies demonstrated no effect. A recent randomized control trial demonstrated improved cecum insertion time, lower patient pain score and easier scope manipulation with glucagon supplementation but failed to produce a significant clinical impact due to a small sample size (30 subjects in each study group).

We propose to definitively demonstrate the positive effect of glucagon during colonoscopy by performing a placebo-controlled randomized clinical trial involving a large sample size. We aim to evaluate cecum intubation time, total procedure time, adenoma detection rate, degree of spasm, adequacy of visualization, and patient pain score. We will also determine blood glucose level at the end of the procedure to determine the effect of glucagon therapy during colonoscopy. The primary endoscopist for this study, [name], performs or supervises ~15 colonoscopies per week therefore we can expect to enroll at least 300 outpatient subjects over a one-year period.

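### Cecal intubation time is the implied primary outcome but is never named as such, and the 11 listed aims are tested with no rule on which result counts as confirmed

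*Combined protocol and SAP*

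**What the plan says.** - **Section 8.2** opens with "Identify whether glucagon administration during colonoscopy improves the following" and then numbers 11 outcomes without ranking them. Cecal intubation time is aim 1. Aim 4 is "Adenoma detection rate (i.e. the total number of polyps and adenomas per patient procedure").
- **Section 8.3** is the whole analysis plan: "Matched student t-test will be used for continuous variables and the Chi-square test will be used for categorical variables", followed by "The UCSF Department of Epidemiology and Biostatistics will be involved in the formal statistical analysis". It has no primary outcome, testing order, division of alpha or adjustment.
- **Section 8.1** gives reduced colonic spasm as the mechanism, then lists the expected benefits: "improved diagnostic yield (improved adenoma detection rate), faster procedure times, and improved patient and endoscopist experience". Adenoma detection comes first.
- **Section 7.1** says the trial "studies key parameters of a colonoscopy such as cecal intubation time, withdrawal time, total procedure time, adenoma detection rate" and three further items, seven in all and unranked.
- **Section 9.1** states: "We propose to definitively demonstrate the positive effect of glucagon during colonoscopy by performing a placebo-controlled randomized clinical trial". Its next sentence reads "We aim to evaluate cecum intubation time, total procedure time, adenoma detection rate, degree of spasm, adequacy of visualization, and patient pain score", which is six outcomes, unranked. End-of-procedure blood glucose follows.
- **Section 10.4** sizes the trial on cecal intubation time alone (294 s against 370 s, SD 140 s, power 0.9, alpha 0.05, 67 per arm). It does not call that outcome primary.
- **Sections 10.1 and 10.2** give 200 subjects, which is 100 per arm at the 1:1 allocation in 14.1.
- **Section 16.5** gives the purpose of measuring blood glucose: to describe the side-effect profile of glucagon.

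**The concern.** The sections point to different headline outcomes. The sample size and the order of the lists point to cecal intubation time, the stated hypothesis points first to adenoma detection, and 8.2 treats all 11 aims alike. Section 9.1 promises a confirmatory result without saying which outcome has to deliver it.

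With 11 tests at 0.05 and no ranking, a chance finding on any one of them could be reported as a demonstrated benefit of glucagon without departing from the written plan. That matters more here because 9.1 presents this trial as the one that settles conflicting results from four small studies. Involving a biostatistics department is sensible, but it does not supply the missing rule.

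**Working it through.** **1. The plan's own sizing figure.** Inputs from 10.4: difference 370 − 294 = 76 s; SD 140 s; alpha 0.05 (sidedness not stated, two-sided assumed); power 0.9. The standardised difference is 76/140 = 0.543.

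- Normal approximation: n = 2 × [140 × (1.960 + 1.282)/76]² = 71.3, so 72 per arm.
- Two-sample t-test: 72.3, so 73 per arm.
- One-sided 0.05 would give 59.

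The stated 67 is not reproduced. At 67 per arm the t-test has 88% power (0.877). At the planned 100 per arm it has 97% (0.969).

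**2. Chance of a false positive over the 11 aims.** Assume each aim is tested two-sided at 0.05, the only alpha in the documents, and that glucagon affects none of them.

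Independent tests:
- any false positive: 1 − 0.95^11 = 0.431
- at least one favouring glucagon: 1 − 0.975^11 = 0.243

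The aims are related (the three times overlap, and the grades come from the same raters), so independence overstates the risk. With a common correlation ρ ≥ 0 between the test statistics and c = 1.960:

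- any: 1 − ∫ φ(u) [Φ((c − √ρ·u)/√(1−ρ)) − Φ((−c − √ρ·u)/√(1−ρ))]^11 du
- favouring glucagon: 1 − ∫ φ(u) [Φ((c − √ρ·u)/√(1−ρ))]^11 du

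| Assumed ρ | Any false positive | One favouring glucagon |
|---|---|---|
| 0 | 0.431 | 0.243 |
| 0.3 | 0.375 | 0.191 |
| 0.5 | 0.304 | 0.152 |
| 0.7 | 0.223 | 0.111 |

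A less uniform pattern gives similar values. With correlation 0.7 within times (aims 1-3), endoscopist grades (6-8) and patient grades (9-11), and 0.2 for all other pairs, simulation gives 0.35 and 0.18.

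If the effect on cecal intubation time is real, ten null aims remain. The independent figure becomes 1 − 0.95^10 = 0.401, so the problem hardly shrinks.

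**3. What the remedies need.**
- *One primary at 0.05.* The 73 per arm from step 1 lies within the planned 100.
- *Holm over the ten secondary aims.* The first step is at 0.05/10 = 0.005. The standardised difference detectable with 80% power at 100 per arm rises from 0.40 (alpha 0.05) to 0.52 (alpha 0.005).
- *All 11 aims as equal claims with Bonferroni.* Alpha is 0.05/11 = 0.00455. The 76 s effect then needs 116 per arm by the normal formula, or 232 in total, which exceeds the planned 200.

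**The case against.** The best reply is that the primary outcome is plain to any reader: cecal intubation time heads three lists and is the only outcome with a target difference, SD, alpha and power. Moving to another headline would be noticed. Much of this stands. A reader might infer that the plan gives no hint of a primary and leaves a free choice after unblinding, and the documents do not support that. What is missing is a commitment, and the order of benefits in 8.1 pulls the other way. The registry record behind the number in 5.8 was not available, so the point concerns this document only.

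Other inferences also go too far:

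- *That blood glucose is a twelfth efficacy test of undefined status.* Section 16.5 gives it a side-effect purpose, which fits its absence from a list of hoped-for improvements. It is not counted above.
- *That 9.1 names no outcomes.* The sentence after the promise names six. It ranks none of them.
- *That 8.1 opens with adenoma detection.* It opens with reduced spasm. Adenoma detection is the first benefit expected to follow.
- *That the trial is underpowered for adenoma detection.* The documents give no mean, spread or target effect for it, so its power cannot be calculated from them.

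It may also be said that the remedy adjusts nothing and only labels. That is so, but the label controls the error rate of the one confirmatory claim and limits what can be said of the rest.

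**Conclusion.** The concern holds in this limited form. The plan has an implied primary outcome that it never names, and it has no rule on which of 11 aims can support a confirmed claim. If each aim is tested at 0.05, the global-null chance of at least one false positive is 22-37%, and of one favouring glucagon 11-19%. The correlations of 0.7 to 0.3 behind these ranges are assumptions, as is two-sided testing of every aim. Independence gives the upper figures of 43% and 24%. The finding itself does not depend on these numbers, because the omission is visible in 8.1 to 8.3. It should be corrected before unblinding. It does not invalidate the design, since the sizing already supports a sensible primary outcome.

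**What to change.** In 8.1 to 8.3, state that cecal intubation time (aim 1) is the single primary outcome, tested at two-sided alpha 0.05. State that aims 2 to 11 are secondary, reported as differences with 95% confidence intervals and not claimed as confirmed effects. Report end-of-procedure blood glucose as a safety measurement, in line with 16.5 and outside the efficacy outcomes. In 9.1, limit *definitively* to the primary outcome.

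Two choices remain with the investigators:
- If confirmatory secondary claims are wanted, specify Holm over the ten secondary aims in advance and accept the larger detectable difference shown above.
- If adenoma detection is meant to be primary, say so and redo 10.4 for it, using the per-patient count that 8.2 defines or a revised definition.

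The cost is one paragraph in 8.1 to 8.3 and one sentence in 9.1, with no extra patients or data. The loss is that secondary results, including adenoma detection, can no longer be presented as confirmed benefits. The figure in 10.4 should not be taken as sound on this account: its inputs need 73 per arm for 90% power, not 67. The planned 100 per arm covers the gap.

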## 9.0 Background

### 9.1 Background:

Colonoscopy is the most commonly performed surgical procedure by gastroenterologists in the United States and is most commonly used for the screening, detection and removal of benign polyps, neoplastic polyps and colon cancer. The National Polyp Study demonstrated a significant decrease in the incidence of colorectal cancer following endoscopic removal of polyps detected during screening colonoscopy. Currently, only 50% of Americans at risk for development of colorectal cancer are being screened with a colonoscopy and attempts to increase the rate of screening will be limited by the total number of colonoscopies that are performed daily in the United States. Thus, identifying interventions that decrease the duration of colonoscopy while maintaining its effectiveness in identifying pre-cancerous polyps can lead to a significant clinical impact.

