5. The nursing staff will record, as per standard procedure during colonoscopy, the following: cecum intubation time, colonoscope withdrawal time, total procedure time, use of sedatives for the procedure. The endoscopist will rate the difficulty in scope manipulation, adequacy of visualization and the severity of spasms experienced during the colonoscopy. [name] will review the pathology results and records adenoma detection rate for each subject.

6. The patient will be discharged home according to discharge criteria already established in the outpatient GI endoscopy suite. They will be provided a questionnaire and a pre-addressed envelope prior to discharge.

7. The following day, patients will be asked by mail contact to rate pain, abdominal fullness, and willingness to accept a future colonoscopy if clinically indicated and return their questionnaire in the pre-addressed envelope provided. These will be done according to the enclosed questionnaire sheets.

If you have a procedure table, attach it to the submission with your other study documents.

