### 16.3 Benefits to subjects:

- Yes  No

If yes, describe:

If the patient is randomized to receive glucagon, the colonoscopy may take less time, require less intravenous sedation and/or find more polyps.

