#### 16.4 Benefits to society:

Potential improvement of a procedure used widely in healthcare. The improvement may lead to better polyp detection rate, less operator fatigue and improved patient comfort.

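### Item 4 of section 8.2 defines the adenoma detection rate as a count pooling all polyps with adenomas, so it cannot by itself test the adenoma hypothesis in 8.1

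*Combined protocol and SAP*

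**What the plan says.** - **Section 8.1** gives the expected effects as "improved diagnostic yield (improved adenoma detection rate), faster procedure times, and improved patient and endoscopist experience". It does not define the adenoma detection rate.
- **Section 8.2, item 4** holds the only definition: "Adenoma detection rate (i.e. the total number of polyps and adenomas per patient procedure".
- **Section 9.1** describes colonoscopy as used for "screening, detection and removal of benign polyps, neoplastic polyps and colon cancer", so it separates benign from neoplastic polyps. It seeks interventions that "decrease the duration of colonoscopy while maintaining its effectiveness in identifying pre-cancerous polyps". Its list of outcomes includes "adenoma detection rate, degree of spasm, adequacy of visualization, and patient pain score" but no separate polyp count.
- **Section 14.1, step 5** says that a named team member "will review the pathology results and records adenoma detection rate for each subject". It does not say which lesions count or on what scale.
- **Sections 16.3 and 16.4** speak of polyps in general: "the colonoscopy may take less time, require less intravenous sedation and/or find more polyps" and "The improvement may lead to better polyp detection rate, less operator fatigue and improved patient comfort".
- **Section 8.3** assigns a t-test to continuous variables and a chi-square test to categorical ones. It does not say where item 4 falls.

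**The concern.** The hypothesis concerns adenomas, and the background makes precancerous lesions the target. The outcome that has to carry the hypothesis is a total that takes in every polyp. Three things follow.

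1. If glucagon changed only the yield of non-adenomatous polyps, the trial could report an adenoma effect that is absent.
2. If it changed only adenomas, the other polyps would dilute the effect.
3. Two analysts could score the same pathology report differently, because the definition does not say how an adenoma, which is itself a polyp, enters a total of polyps and adenomas. With no fixed rule, that choice could be made after the results are known.

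Polyp yield is a legitimate aim, as 16.3 and 16.4 show, but neither 8.2 nor 9.1 lists it as an outcome of its own.

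**Working it through.** The plan states no rate, mean, standard deviation or power for this outcome, so there is no figure to reproduce. The main check is a comparison of the texts. The calculations only show direction.

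**1. Texts side by side.** Section 8.1 uses the term undefined. Item 4 of 8.2 equates it, through its i.e., with a single total covering polyps and adenomas. Step 5 of 14.1 repeats the label without a numerator or scale. No section restricts the count to adenomas or calls for two tallies.

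**2. Scoring one patient.** Take 2 adenomas and 1 other polyp. Adenomas only gives 2. Each lesion counted once gives 3. Adding 3 polyps and 2 adenomas gives 5.

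**3. A shift with no adenoma effect.** Assume 0.5 adenomas per procedure in both arms, and other polyps at 0.5 on placebo and 0.8 on glucagon. The pooled means are 0.5 + 0.5 = 1.0 and 0.5 + 0.8 = 1.3, a 30% rise with no adenoma difference.

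**4. Dilution.** Let placebo means be A = 0.5 adenomas and B other polyps. If adenomas alone double, the pooled ratio is (2A + B)/(A + B) = (1 + B)/(0.5 + B):
- B = 0.25: 1.25/0.75 = 1.67
- B = 0.5: 1.5/1.0 = 1.50
- B = 1.0: 2.0/1.5 = 1.33

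The true adenoma ratio is 2.0 in each case.

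**5. Simulated chance of p < 0.05.** The 200 subjects in 10.1, allocated 1:1 (14.1), give about 100 per arm. The assumed inputs are A = 0.5; B = 0.25, 0.5 or 1.0; independent negative binomial counts with k = 0.5; and an unpaired t-test. There were 100,000 runs.

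| Glucagon effect | Pooled count, each lesion once (B = 0.25 / 0.5 / 1.0) | Adenoma count |
|---|---|---|
| Other polyps ×1.5 only | 0.11 / 0.20 / 0.32 | 0.05 |
| Other polyps ×2 only | 0.27 / 0.53 / 0.76 | 0.05 |
| Adenomas ×1.5 only | 0.25 / 0.20 / 0.13 | 0.31 |
| Adenomas ×2 only | 0.64 / 0.53 / 0.35 | 0.73 |
| Both ×1.5 | 0.48 / 0.55 / 0.59 | 0.31 |
| Both ×2 | 0.92 / 0.96 / 0.97 | 0.73 |

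If adenomas are counted twice, the first two rows become 0.07 / 0.12 / 0.22 and 0.13 / 0.30 / 0.59.

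**6. Sensitivity to the assumptions.** These runs (20,000 each) count each lesion once.
- *Dispersion, other polyps only.* With k = 1, the ×1.5 row becomes 0.13 / 0.26 / 0.46 and the ×2 row 0.35 / 0.68 / 0.92. With Poisson counts they become 0.16 / 0.37 / 0.76 and 0.47 / 0.89 / 1.00.
- *Correlation within patients.* With a shared patient-level effect (k = 0.5), the false-signal range is about 9% to 23% for ×1.5 and 20% to 60% for ×2. Pooled power is about 52% down to 23% when only adenomas double, and about 79% to 86% when both double.

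The sizes move and the direction does not. The adenoma mean of 0.5 was not varied.

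**7. Proportion with at least one adenoma.** With mean m, this is 1 − (k/(k + m))^k. For k = 0.5:
- m = 0.5: 1 − (0.5/1.0)^0.5 = 29.3%
- m = 1.0: 1 − (0.5/1.5)^0.5 = 42.3%

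The chi-square test then has power of about 0.48 for a doubling, against 0.73 for the adenoma count.

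**The case against.** The strongest case against has four parts.

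- **No two definitions conflict.** Section 8.1 leaves the term undefined and 8.2 supplies its meaning. The broader phrase in 8.1 is diagnostic yield, and 16.3 and 16.4 suggest that the investigators use these terms loosely for lesion yield. This is true, but if item 4 does define the term, non-adenomatous polyps count as adenoma detection and the adenoma claim has no outcome of its own.
- **Two separate tallies may have been meant.** Step 5 takes the data from pathology, which fits that reading. The adenoma tally would then be clean and only the wording would need repair. This reading cannot be excluded, but no section states it and item 4 speaks of one total.
- **The harm needs an effect that differs by lesion type.** The stated mechanism is less spasm, and nothing in the documents says that this favours one histology. That stands: with equal ratios pooling causes no distortion and gains power. A pooled result cannot show which case applies.
- **The illustration rests on assumed rates, dispersion and independence.** This also stands. A shared patient effect lowers the false-signal figures and worsens the dilution, so the printed ranges understate the uncertainty.

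Item 4 is also only one of 11 aims and does not drive the sample size, which limits the consequence.

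**Conclusion.** The concern holds. Followed as written, item 4 of 8.2 puts non-adenomatous polyps into the outcome labelled adenoma detection rate, and nothing elsewhere corrects this. A result on that outcome could not by itself support the adenoma claim in 8.1. This conclusion comes from the text and depends on none of the simulated figures.

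On the assumed rates, the pooled count would give a false adenoma signal in about 11% to 32% of trials for a 50% rise in other polyps alone, and in 27% to 76% for a doubling, against the nominal 5%. A true doubling of adenomas alone would appear as a ratio of 1.67 down to 1.33. These figures show direction and are not properties of this trial. The point should be fixed, but it does not undermine the trial as a whole.

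**What to change.** 1. In item 4 of 8.2, define the outcome as the number of histologically confirmed adenomas per procedure, each counted once, and name it as a count.
2. List all polyps per procedure, each lesion counted once, as a separate outcome. This keeps the yield aim of 16.3 and 16.4.
3. In step 5 of 14.1, record for each subject the number of adenomas and the number of other polyps from the pathology review already planned. State where cancers are recorded, since 9.1 names them.
4. State in 8.3 which test applies. As numeric outcomes, both counts would fall under the rule for continuous variables.
5. Optionally, add the proportion of patients with at least one adenoma, compared by the chi-square test, and note its lower power.

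**Cost.** These are wording changes in 8.2, 8.3 and 14.1. No new procedure is needed, and the sample size in 10.4 is unaffected because it rests on cecal intubation time. The downsides to state are one more outcome beside the present 11 aims (two with the optional proportion), and less power than the pooled count if glucagon raises all lesion types alike (73% against 92% to 97% for a doubling on the assumed rates).
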